2.2 Secondary Objective and Endpoint

Objectives	Endpoints
To assess the rate of surgical cure with and without pembrolizumab.	Proportion of patients who achieve a sustained complete response following second evacuation and no further anti-cancer therapy, defined as normalisation of hCG and no rise by 1 year post procedure.
To assess the safety of a single dose of pembrolizumab prior to second evacuation versus second evacuation alone.	Incidence of adverse effects of second evacuation and pembrolizumab within 30 days and 12 weeks respectively, assessed by Common Terminology Criteria for Adverse Events (CTCAE v5.0, 27 Nov 2017).

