5.5 Visit Schedule

Table 2: Schedule of Assessments: Second evacuation only

Procedure	Pre-screening	Baseline/screening Day -3 to 0	Day 7 ¹	2 weeks post evacuation ²	6 weeks post evacuation ²	12 weeks post evacuation ²	Every 2 weeks post evacuation until normalisation of hCG	Every month following normal hCG and until 1 year post evacuation
Informed Consent		X						
Medical History & Demographics		X						
Physical Exam		X		X	X			
Performance Status		X		X	X			
Vital Signs		X						
Haematology	X							
Biochemistry	X							
Coagulation	X							
Viral Screen (Hep B, Hep C, HIV)	X							
Thyroid Function Tests and Cortisol		X						
Tumour marker blood hCG	X						X	
Research Blood Sample		X		X	X	X		
Archival Tissue		X						
Imaging - Chest X-ray	X							
Imaging - Uterine ultrasound scan	X		X					
Randomisation		X						
Surgical evacuation			X					
Urine hCG							X	X
Adverse Events				X	X	X		
Concomitant Medications		X						

RESOLVE	C/43/2022	Imperial College London	v2.0 10 th July 2023
---------	-----------	-------------------------	------------------------------------

1. Visit is permitted to be performed two days prior or after scheduled timepoint.
2. Visit is permitted to be performed three days prior or after scheduled timepoint.

Table 3: Schedule of Assessments: Pembrolizumab arm

Procedure	Pre-screening	Baseline/Screening Day -3 to 0	Day 0	Day +7 ¹	Day +11 ¹	Day +14 ¹	2 weeks post evacuation ²	6 weeks post evacuation ²	12 weeks post evacuation ²	Every 2 weeks post evacuation until normalisation of hCG	Every month following normal hCG and until 1 year post evacuation
Informed Consent		X									
Medical History & Demographics		X									
Physical Exam		X			X		X	X	X		
Performance Status		X			X		X	X	X		
Vital Signs		X			X						
Haematology	X				X			X	X		
Biochemistry	X				X			X	X		
Coagulation	X				X			X	X		
Viral screen (Hep B, Hep C, HIV)	X										
Thyroid Function Tests and Cortisol		X						X	X		
Tumour marker blood hCG	X			X	X					X	
Research Blood sample		X				X	X	X	X		
Archival Tissue		X									
Imaging – Chest X-ray	X										
Imaging – Uterine ultrasound scan	X					X					
Imaging – Optional Magnetic Resonance Imaging			X ³			X ⁴					
Randomisation		X									
Pembrolizumab			X								

RESOLVE	C/43/2022	Imperial College London	v2.0 10 th July 2023
---------	-----------	-------------------------	------------------------------------

Surgical evacuation						X					
Urine hCG										X	X
Adverse Events					X		X	X	X		

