5.7 Follow-up

Following second evacuation, patients in both arms will undergo standard of care urine and blood hCG monitoring every 2 weeks until hCG normalisation and then monthly urine hCG measurement for up to 1 year post evacuation. Failure of second evacuation to result in disease control is defined as per national guidelines (rise or plateau in hCG, hCG over 20,000 IU/L at 4 weeks, heavy vaginal bleeding). Patients will additionally have a clinical review and toxicity check at 2, 6 and 12 weeks post evacuation.

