8.3.4 Safety Analysis

Safety data analysis will be conducted on all subjects randomised within the trial. Data will be collected on the number of patients who are withdrawn from the study in order to commence chemotherapy due to tumour progression. The number and proportion of patients who experience complications arising from second evacuation will be reported. In the intervention arm, the number and percentage of subjects experiencing an AE and the number of events will be reported. Information regarding severity will be examined with a focus on Grade 3-5 events using the Common Terminology Criteria for Adverse Events (CTCAE v5.0).

RESOLVE	C/43/2022	Imperial College London	v2.0 10 th July 2023
---------	-----------	-------------------------	------------------------------------

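### Section 8.3.4 counts all-cause adverse events in the intervention arm only, so this part of the comparative safety objective has no control-arm counterpart

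*Protocol*

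**What the plan says.** The safety objective in Protocol section 2.2 is comparative: "To assess the safety of a single dose of pembrolizumab prior to second evacuation versus second evacuation alone". The endpoint paired with it is worded by source of harm: "Incidence of adverse effects of second evacuation and pembrolizumab within 30 days and 12 weeks respectively".

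Section 8.3.4 sets out the analysis. It opens with the population: "Safety data analysis will be conducted on all subjects randomised within the trial". It then gives three summaries of AEs:

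- Surgical complications, no arm named: "The number and proportion of patients who experience complications arising from second evacuation will be reported".
- Overall AE counts, one arm named: "In the intervention arm, the number and percentage of subjects experiencing an AE and the number of events will be reported".
- Severity, no arm named: "Information regarding severity will be examined with a focus on Grade 3-5 events".

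On data collection, the control-arm schedule in section 5.5 ("Table 2: Schedule of Assessments: Second evacuation only") has an adverse-event row marked at 2, 6 and 12 weeks after evacuation. Section 5.7, which covers both arms, agrees: "Patients will additionally have a clinical review and toxicity check at 2, 6 and 12 weeks post evacuation". Section 7.4 asks for every adverse event to be reported and makes no exception for controls.

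**The concern.** A randomised trial that sets out to compare safety between two arms should give its main AE summary for both. Here the overall count is specified for the arm that receives the drug and for no other, although the control data will be in the database.

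Intervention patients also undergo the evacuation and have the same disease as controls. Section 8.3.4 counts subjects with an AE, not with a drug-related AE, and the definition in 7.1 does not require a causal link. A one-arm count is therefore a mixture of background, surgical and drug-related events. The randomised control arm is the design's own means of removing the first two, and the stated analysis does not use it for this count. Section 1.1 says that the results could lead directly to a new standard of care or to a larger study, so an AE rate with no reference could be misread in either direction.

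**Working it through.** The protocol states no figure for AE incidence, so there is nothing to reproduce. The check is a comparison of sections, followed by an illustration.

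**Step 1: objective, data and analysis side by side**

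| Element | Intervention arm | Control arm | Source |
|---|---|---|---|
| Part of the safety comparison | yes | yes | 2.2 |
| In the safety population | yes | yes | 8.3.4, first sentence |
| AEs collected at 2, 6, 12 weeks after evacuation | yes | yes | Tables 2 and 3; 5.7 |
| Evacuation complications summarised | yes | yes (no arm limit) | 8.3.4 |
| Severity review, Grade 3-5 | not limited | not limited | 8.3.4 |
| Patients with any AE, and number of events | yes | **not specified** | 8.3.4 |

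Only the last row fails. It is at odds with the objective and with the section's own opening sentence on population. Section 8.3.3 refers safety analysis to 8.3.4, so no other section fills the gap.

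**Step 2: what the missing comparator hides**

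Arm sizes are 10 and 10 (Table 1). The protocol gives no AE rates, so the counts below are assumptions. One-arm intervals are exact (Clopper-Pearson). Intervals for the difference p1 − p0 are Newcombe's, built from the Wilson limits (l, u) of each arm:

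- lower = (p1 − p0) − √[(p1 − l1)² + (u0 − p0)²]
- upper = (p1 − p0) + √[(u1 − p1)² + (p0 − l0)²]

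For 5/10 against 2/10, the Wilson limits are 0.237 to 0.763 and 0.057 to 0.510. Then:

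- lower = 0.30 − √(0.263² + 0.310²) = 0.30 − 0.407 = −0.107
- upper = 0.30 + √(0.263² + 0.143²) = 0.30 + 0.300 = 0.600

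| Intervention | Control | 8.3.4 as written reports | Difference in points (95% CI) |
|---|---|---|---|
| 5/10 | 2/10 | 5/10 (exact 19 to 81%) | 30 (−11 to 60) |
| 5/10 | 5/10 | 5/10 (exact 19 to 81%) | 0 (−37 to 37) |
| 8/10 | 2/10 | 8/10 (exact 44 to 97%) | 60 (16 to 80) |

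The first two rows give the same output under the stated plan, although they describe different safety findings.

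**Step 3: would a plain by-arm table be fair?**

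Not without care, because the schedules differ:

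- Table 3 has an AE check at Day +11, before evacuation. Table 2 has none before evacuation.
- After randomisation, haematology, biochemistry and coagulation (Day +11, 6 and 12 weeks) and thyroid function and cortisol (6 and 12 weeks) are scheduled only in Table 3. Controls have blood hCG and research blood samples, which are not safety laboratory tests.

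Counting everything from randomisation would therefore inflate the intervention arm through closer observation. The AE checks at 2, 6 and 12 weeks after evacuation are common to both arms.

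**The case against.** The best defence is that the analysis follows the endpoint rather than the objective. The endpoint attributes harms to evacuation and to pembrolizumab separately. Section 8.3.4 does likewise: surgical complications for everyone, AEs for the arm that gets the drug. Section 7.1 defines an AE in a subject given a medicinal product, and controls receive no trial drug. Section 7.2 has the investigator grade causality, so there is some means of attribution. This explains how the wording arose, but only in part. The sentence counts any AE and not those judged related, Table 2 has an adverse-event row for controls, and causality grading in an open-label trial does not replace a randomised comparison.

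A second defence is that by-arm tables are normally left to a statistical analysis plan, which is not at hand, and that 8.3.4 does not exclude a control-arm table. That would answer a complaint about silence. Here the protocol names one arm, and an analysis plan that followed it literally would carry the restriction forward.

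A third is that ten per arm is too few to compare. Section 8.1.3 confirms that the trial was not sized for the comparison of arms. This stands as a reason to be descriptive and not to test. It is not a reason to omit the comparator, since the one-arm percentage is imprecise too.

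A reader might also infer that the safety objective cannot be answered at all, or that AE data from half of the randomised patients go unreported. The documents do not support that: control AEs that are evacuation complications fall under a summary with no arm limit, and the Grade 3-5 review is not confined to one arm. Nor would it be right to infer that controls have no scheduled blood tests after randomisation. They have hCG and research bloods, and only the safety laboratory panels are missing.

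**Conclusion.** The point holds for overall AE counts. Section 8.3.4 specifies patients with any AE, and number of events, for 10 of the 20 planned patients, although the objective is comparative and the control-arm AEs are collected. Followed as written, the plan gives this count no randomised reference, and the excess over surgery and disease cannot be read from it.

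The effect on the safety conclusions cannot be sized from the protocol, which gives no expected AE rates; the counts in the illustration are assumptions. The primary feasibility endpoints are not affected. The correction is worth making before analysis because the data will already exist. The conclusion rests on the protocol text alone; a by-arm table in an unseen analysis plan would close the gap in practice but would leave 8.3.4 to be aligned with it.

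**What to change.** In 8.3.4, change the opening of the overall AE sentence so that it applies to each arm, and specify:

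- By arm, descriptively: patients with any AE (n, %), patients with a Grade 3-5 AE (n, %), and number of events, over the shared visits at 2, 6 and 12 weeks after evacuation. Give 95% confidence intervals for the percentages. A difference with its interval may be added, but no test is needed.
- Separately: AEs in the pembrolizumab arm before evacuation (the Day +11 check), since controls have no matching check.
- Separately: events found only by laboratory test, with a note that haematology, biochemistry, coagulation and thyroid/cortisol tests after randomisation are scheduled only in Table 3.

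The reporting of evacuation complications can stay as it is.

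The cost is a reworded paragraph and a few extra table rows and columns. No new visits, tests or patients are needed. The intervals will be wide at 10 per arm (even 0/10 has an exact upper limit of 31%), and the text should say that the comparison is descriptive.

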9. REGULATORY, ETHICAL AND LEGAL ISSUES

9.1 Declaration of Helsinki

The investigator will ensure that this study is conducted in full conformity with the 1964 Declaration of Helsinki and all subsequent revisions.

9.2 Good Clinical Practice

The study will be conducted in accordance with the guidelines laid down by the International Conference on Harmonisation for Good Clinical Practice (ICH GCP E6 guidelines).

9.3 Research Ethics Committee (REC) Approval

(i) Initial Approval

Prior to the shipment of IMP and the enrolment of participants, the REC must provide written approval of the conduct of the study at named sites, the protocol and any amendments, the Participant Information Sheet and Consent Form, any other written information that will be provided to the participants, any advertisements that will be used and details of any participant compensation.

(ii) Approval of Amendments

Proposed amendments to the protocol and aforementioned documents must be submitted to the REC for approval. Amendments requiring REC approval may be implemented only after a copy of the REC's approval letter has been obtained.

Amendments that are intended to eliminate an apparent immediate hazard to participants may be implemented prior to receiving Sponsor or REC approval. However, in this case, approval must be obtained as soon as possible after implementation.

The sponsor trials team will make amendments and make the decision to amend the protocol and decide whether changes are substantial or non-substantial, with support from the Protocol Development Group where applicable. Changes will be communicated to stakeholders, including participating sites, electronically and be version controlled according to tracked changes and in accordance with the relevant standard operating procedures. The amended protocol will be reviewed by all members of the Protocol Development Group prior to finalising.

(iii) Annual Progress Reports

Annual Progress Reports will be submitted to the Research Ethics Committee (REC) and the Sponsor in accordance with local / national requirements. The Annual Progress Report will also detail all SAEs recorded.

RESOLVE	C/43/2022	Imperial College London	v2.0 10 th July 2023
---------	-----------	-------------------------	------------------------------------

(iv) End of Trial Notification

The REC will be informed about the end of the trial, within the required timelines. The end of trial notification will be submitted within 90 days of the end of trial definition being met. In the event of a premature halt of the trial, the timeframe is 15 days, and the reasons should be clearly explained in the notification.

9.4 Regulatory Authority Approval

The study will be performed in compliance with UK regulatory requirements. Clinical Trial Authorisation from the appropriate Regulatory Authority must be obtained prior to the start of the study. In addition, the Regulatory Authority must approve amendments prior to their implementation (as instructed by the Sponsor), receive SUSAR reports and DSURs, and be notified of the end of the trial.

This study has Clinical Trials Authorisation from the UK Competent Authority; MHRA. Reference: CTA 19174/0438/001-0001

9.5 HRA approval

Health Research Authority (HRA) approval will be obtained prior to starting the study. Each participating site will confirm capacity and capability prior to commencing. The HRA and all participating sites also need to be notified of all protocol amendments to assess whether the amendment affects the institutional approval for each site.

9.6 Other Required Approvals

The procedures are compliant with the Ionising Radiation (Medical Exposure) Regulations, and appropriate review by a Medical Physics Expert and Clinical Radiation Expert will be undertaken before the study commences.

9.7 Non-Compliance and Serious Breaches

All protocol deviations and protocol violations will be reported via the eCRF and reviewed by the Chief Investigator and reported to the Research Governance and Integrity Team (RGIT) on a monthly basis.

An assessment of whether the protocol deviation/violation constitutes a serious breach will be made.

A serious breach is defined as:

A breach of the conditions and principles of GCP in connection with a trial or the trial protocol, which is likely to affect to a significant degree:

- The safety or physical or mental integrity of the UK trial participants; or
- The overall scientific value of the trial

RESOLVE	C/43/2022	Imperial College London	v2.0 10 th July 2023
---------	-----------	-------------------------	------------------------------------

RGIT will be notified within 24 hours of identifying a likely Serious Breach. If a decision is made that the incident constitutes a Serious Breach, this will be reported to the MHRA and REC within 7 days of becoming aware of the serious breach.

9.8 Insurance and Indemnity and Sponsor

Imperial College London holds negligent harm and non-negligent harm insurance policies which apply to this study.

Imperial College London will act as the main Sponsor for this trial. Delegated responsibilities will be assigned to the NHS trusts taking part in the trial.

9.9 Funding

Funding for this study has been provided by the Imperial Biomedical Research Centre and the Cancer Treatment and Research Trust Charity. Funding for the translational aspects of the study will be from Cancer Research UK. Funding allocated to the sites is detailed in the participant site agreement. Requests and queries regarding payment should be sent to [contact],

9.10 Trial Registration

The study will be registered on the following trial databases in accordance with requirements of the International Committee of Medical Journal Editors (ICMJE) regulations:

- Clinicaltrials.gov
- Cancer Research UK
- EC Trial Finder

9.11 Informed Consent

Consent to enter the study must be sought from each participant only after a full explanation has been given, an information leaflet offered and time allowed for consideration. Signed participant consent should be obtained. The right of the participant to refuse to participate without giving reasons must be respected. After the participant has entered the trial, the clinician remains free to give alternative treatment to that specified in the protocol at any stage if he/she feels it is in the participant's best interest, but the reasons for doing so should be recorded. In these cases, the participants remain within the study for the purposes of follow-up and data analysis. All participants are free to withdraw at any time from the protocol treatment without giving reasons and without prejudicing further treatment.

RESOLVE	C/43/2022	Imperial College London	v2.0 10 th July 2023
---------	-----------	-------------------------	------------------------------------

9.12 Contact with General Practitioner

It is the investigator's responsibility to inform the participant's General Practitioner (*where applicable*) by letter that the participant is taking part in the study provided the participant agrees to this, and information to this effect is included in the Participant Information Sheet and Informed Consent. A copy of the letter should be filed in the Investigator Site File.

9.13 Participant Confidentiality

The investigator must ensure that the participant's confidentiality is maintained. On the eCRF or other documents submitted to the Sponsors, participants will be identified by a participant ID number only. Documents that are not submitted to the Sponsor (e.g., signed informed consent form) should be kept in a strictly confidential file by the investigator.

The investigator shall permit direct access to participants' records and source documents for the purposes of monitoring, auditing, or inspection by the Sponsor, authorised representatives of the Sponsor, NHS, Regulatory Authorities and RECs.

Data will be transferred to (insert third party name as appropriate or delete)

9.14 Data Protection and Participant Confidentiality

The investigators and study site staff will comply with the requirements of the Data Protection Act 2018 concerning the collection, storage, processing and disclosure of personal information and will uphold the Act's core principles.

9.15 End of Trial

The end of the trial is defined as collection of the last data point for the last participant. Samples taken for translational research will be held under Imperial College Tissue Bank ethics for ongoing work.

9.16 Study Documentation and Data Storage

The investigator must retain essential documents until notified by the Sponsor, and for at least ten years after study completion. Participant files and other source data (including copies of protocols, CRFs, original reports of test results, IMP dispensing logs, correspondence, records of informed consent, and other documents pertaining to the conduct of the study) must be retained. Documents should be stored in such a way that they can be accessed/data retrieved at a later date. Consideration should be given to security and environmental risks.

RESOLVE	C/43/2022	Imperial College London	v2.0 10 th July 2023
---------	-----------	-------------------------	------------------------------------

No study document will be destroyed without prior written agreement between the Sponsor and the investigator. Should the investigator wish to assign the study records to another party or move them to another location, written agreement must be obtained from the Sponsor.

RESOLVE	C/43/2022	Imperial College London	v2.0 10 th July 2023
---------	-----------	-------------------------	------------------------------------

10. DATA MANAGEMENT

10.1 Source Data

All original records and certified copies of original records of clinical findings, observations, or other activities necessary for the reconstruction and evaluation of the trial are classified as source data.

Source data are contained in source documents; these are defined as: original documents, data, and records e.g. hospital medical records, clinical and office charts, laboratory notes, memoranda, patient diaries or evaluation checklists, pharmacy dispensing records, recorded data from automated instruments, copies or transcriptions certified after verification as being accurate copies, microfiches, photographic negatives, microfilm or magnetic media, radiological imaging, patient files, and records kept at the pharmacy, laboratories and any medico-technical departments involved in the clinical trial.

10.2 Language

eCRFs will be in English. Generic names for concomitant medications should be recorded in the CRF wherever possible. All written material to be used by participants must use vocabulary that is clearly understood and be in the language appropriate for the study site.

